10.0 Inclusion and Exclusion Criteria

We will focus on eligible patients with moderate or severe OSA as CPAP is first-line therapy for this population. Because of their similar performance, sleep studies will be performed in patients' homes^{85,86} or in the sleep centers of The MetroHealth System and will be interpreted by registered polysomnographic technologists using standard criteria.⁸⁷ Split night studies will be eligible for inclusion. We will focus on adults as the causes and treatments for OSA are often different in children. To maximize the chances that patients will continue to have the same bed partner throughout the duration of the study, we will only include couples who have been bed partners for at least 6 months. We will focus on English-proficient patients as study interventions have been tailored for English-proficient patients and their bed partners and there are relatively few Spanish-speaking patients in our area. We will exclude patients with conditions that may interfere with their participation or alter their management of OSA. We will also exclude patients who have more complex forms of sleep-disordered breathing requiring other forms of positive airway pressure.

SCREENING INCLUSION CRITERIA	EXCLUSION CRITERIA
-Moderate or severe OSA (Apnea hypopnea index \geq 15 events/hour) -Age \geq 18 years -Bed partner for \geq last 6 months who is willing to participate -English proficient	-Terminal illness -Mentally incompetent -Unstable housing -Need for other forms of positive airway pressure (BPAP or VPAP)

11.0 Vulnerable Populations

This study will not enroll vulnerable populations.

12.0 Local Number of Subjects

This study will enroll 20 African American patients of MetroHealth with OSA and their bed partners.

13.0 Recruitment Methods

Prior to enrollment of the first subject, sealed envelopes containing participant computer-randomized study arm assignment will be created. To assure balanced but unpredictable assignments of participants we will use permuted block randomization, stratified by study site.^{88,89} Study flyers will be distributed to sleep providers to distribute to eligible patients who can contact study staff for enrollment. Research assistants will obtain automated digital reports from EpicCare of patients who have received an at-home or in-lab diagnostic sleep study over the previous 48 hours and an order for initiation of CPAP. They will review EpicCare to verify eligibility (see Table above). Study staff will mail a study brochure and consent form to patients. Those who do not respond within 72 hours will receive a phone call to confirm patient and bed partner eligibility and to explain the study in detail. Upon obtaining verbal confirmation, staff will arrange a date and time to meet with patients and their bed partners in person to obtain written consent and to administer baseline study instruments. After completion of these initial tasks, staff will open envelopes to determine subject study arm assignment. Only the sleep technologist, the research assistants who enroll the patients and the participants will be aware of study arm assignments. Participants will receive ClinCard payments within 1 week of completion of study tasks. Participants will receive \$50 for completion of the baseline, 30-day, and 90-day instruments (\$150 total / participant paid by ClinCard). Participants will also be reimbursed for public transportation or parking.

14.0 Withdrawal of Subjects

Participants will not be withdrawn from the research without their consent. Participants who withdraw from the study will be able to keep their CPAP machine and will continue to receive care at MetroHealth per usual. Their data collected up to the time of withdrawal from the study will continue to be used according to intention to treat methodology.

15.0 Risks to Subjects

Potential risks to participants are (a) discomfort with sleep technologist interactions and (b) breaches of confidentiality. Precautions to minimize these risks are described below. The only alternative is to no participate in the study. However, patients may refuse to interact with study staff, decline to follow their advice, or withdraw from the study at any time.

All interactions with subjects will occur within the MetroHealth System where they receive care. As a result, all the usual approaches to maintain privacy and confidentiality in the health care setting will be observed. We will immediately notify the patients' primary care provider if they are suicidal at any time during the trial so that urgent evaluation and treatment can be arranged.

To protect against breaches of confidentiality, all study-related data to be secured on the password- and firewall-protected servers of The MetroHealth System. These servers are continuously backed up. No participant identifying data will be released or reported publicly.

The project manager and research assistants will have password-protected laptops with encrypted storage to enter study data into RedCap, the secure web-based database manager residing on the servers of The MetroHealth System. No data will reside directly on the laptops, but instated will be backed up to the secure, private servers of The MetroHealth System. These servers are protected by MetroHealth's firewall. Mosio will use HIPAA compliant procedures to securely send and receive data between study participants and RedCap.

16.0 Potential Benefits to Subjects

The risks of the proposed study are minimal as discussed above. Our proposed intervention is designed to improve CPAP adherence among patients with moderate and severe OSA. This approach may lead not only to improved sleep quality for patients and their bed partners, but increased functional status, and increased quality of life.

Participants will receive a CPAP machine and supplies that they keep upon conclusion of the study. They will also receive access to CPAP machine and equipment management.

17.0 Data Management and Confidentiality

Our study database will be stored in RedCap (<https://www.project-redcap.org>),⁹⁰ a secure, open-source software application regularly utilized by [name] research teams. RedCap runs on the MetroHealth server and therefore is HIPAA compliant, provides user-specific data access, and facilitates removal of participant identifying data prior to exporting. It also facilitates double data entry with real-time data validation and data integrity checks. Patient data will be entered directly into the RedCap. Study data will be held for 7 years following study completion. Paper records will be stored in locked filing cabinets within the Center for Reducing Health Disparities (Rammelkamp R209). Mosio will use HIPAA compliant procedures to securely send and receive data between study participants and RedCap.

Because this is a pilot study, a power calculation is not provided.

We will begin our analysis by computing descriptive statistics and using graphical representations to examine all predictor and outcome variables. For each study patient, the primary outcome will be CPAP adherence at 90 days as determined by the mean daily CPAP usage (the total number of hours of CPAP use divided by the number of days observed for the

individual). An intention to treat analytic approach will compare mean daily CPAP usage between intervention and control patients as randomized. Linear mixed effects models using random effects will be used to adjust for clustering of patients within sleep provider. Covariates (fixed effects) will include indicator variables for BMI, AHI, gender, and treatment.⁸⁹ The model assumption that the overall CPAP usage outcome is normally distributed will be tested using the Shapiro-Wilk test. If a significant departure from normality is obtained (and a suitable transformation, such as log, is not found) an alternative approach will be to use a generalized linear (e.g., Poisson regression) model for the overall adherence (CPAP usage rate). A Wald test (with robust estimate of standard error) will be used to test for an intervention effect and a corresponding 95% confidence interval for the intervention effect will be computed. If substantial variability in follow-up times are found (e.g., due to dropout and/or missed visits), a weighting approach (using weights proportional to the number of days observed for each individual in conjunction with the selected model) can be used.

We will perform primary and secondary analyses like those for Aim 1. However, the outcome variables for Aim 2 analyses will be scales and subscales related to quality of sleep (Epworth Sleepiness Scale, PROMIS Sleep Disturbance Index), functional status (Functional Outcomes of Sleep Questionnaire short version), and quality of life (SF-12, Calgary Sleep Apnea Quality of Life Index) for both patients and their bed partners. If these outcome variables are not normally distributed, we will use proportional odds with random effects by study site and sleep provider to test differences in these ordinal data between arms.⁹¹

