We propose to pilot test a couple-oriented intervention in a randomized controlled trial of 20 African American patients diagnosed with moderate to severe OSA and their partners. Half of the patients will receive optimal **usual care currently implemented at MetroHealth**, consisting of sleep therapist-initiated standardized education about OSA, sleep hygiene, and CPAP use; personalized mask fittings; and follow-up at 1 week to troubleshoot problems with CPAP utilization. Participants will follow up with their sleep providers per usual. The remaining patients and their bed partners will receive a **couple-oriented intervention** consisting of guideline-recommended best practices for improving CPAP adherence consisting of sleep therapist-initiated **standardized education for couples** about OSA, sleep hygiene, and CPAP use; personalized mask fittings; and follow-up at 1 week to troubleshoot problems with CPAP utilization. Couples will participate in two couple-oriented support groups led by an African American patient with long standing OSA treated with CPAP and their partner. Patients and partners will receive tailored text messages encouraging adherence. In addition, **couples will receive** five 60-minute **virtual cognitive behavioral couple therapy** sessions with a health psychologist trained in behavioral sleep medicine that will focus on enhancing **couples' knowledge** of CPAP, **patients' self-efficacy** to use CPAP, **couple's relationship dynamics**, and **partners' skill and self-efficacy** in assisting the patient with CPAP adherence.

Primary Aim 1: To determine the impact of a couple-oriented intervention on CPAP adherence.

Hypothesis: Compared to usual care patients, patients who receive the couple-oriented intervention will use CPAP for more hours per night over 90 days (primary outcome).

Primary Aim 2: To determine the impact of a couples-oriented intervention on quality of sleep, functional status, and quality of life of OSA patients and their partners.

Hypothesis: Compared to usual care couples, couples who receive the couple-oriented intervention will have a higher quality of sleep, functional status, and quality of life at 90 days (secondary outcomes).

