4.0 Study Endpoints

Primary Endpoint: Mean CPAP adherence over 90 days

Secondary Endpoints: Mean CPAP adherence over 30 days
Patient and Bedpartner quality of sleep at 90 days
Patient and Bedpartner functional status at 90 days
Patient and Bedpartner quality of life at 90 days

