Patient demographic and medical characteristics (e.g., comorbid conditions) will be obtained directly from EpicCare. Socioeconomic status will be assessed by asking patients about their education, occupation, and income. Patient and bed partner relationship quality will be assessed using the 4-item version of the Dyadic Adjustment Scale (DAS-4), one of the most widely used measures of couple satisfaction in research and clinical practice.⁷⁶ The 6-item Zarit Burden Interview for Dementia Caregivers is one of the most widely used measures of caregiver burden.⁷⁷ OSA severity will be assessed using the apnea-hypopnea index, the time spent with oxyhemoglobin saturation < 90%, and the lowest value of oxyhemoglobin saturation each retrieved from the polysomnogram report.⁷⁸ All participants will be given an autotitrating CPAP machine that can be monitored remotely. The device will upload objective adherence data to RedCap each morning following use. **Adherence is the average nightly use of CPAP from baseline to designated follow-up times (30 days, 90 days).**

Instruments to measure OSA knowledge and beliefs, depression, sleepiness, quality of sleep, quality of life, self-efficacy to use CPAP, and degree of bed partner involvement in CPAP adherence will be completed by all study participants at **baseline, 30 days, and 90 days**. These instruments have demonstrated reliability and validity and have been used in previous

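### The primary outcome divides CPAP hours by each patient's days observed rather than by 90 nights, so nights after withdrawal can drop out, and weighting by days observed does not repair this

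*Protocol*

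**What the plan says.** Section 17.0 fixes the formula for the primary outcome as "the total number of hours of CPAP use divided by the number of days observed" for the individual. It does not say what makes a day observed. If follow-up times vary substantially, for example through dropout or missed visits, it allows a weighted analysis "using weights proportional to the number of days observed for each individual".

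Other sections describe a common window. Section 4.0 has "Primary Endpoint: Mean CPAP adherence over 90 days". Section 6.0 has "Adherence is the average nightly use of CPAP from baseline to designated follow-up times (30 days, 90 days"). The Aim 1 hypothesis in section 2.0 likewise speaks of hours per night over 90 days.

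On withdrawal, section 14.0 states: "Their data collected up to the time of withdrawal from the study will continue to be used according to intention to treat methodology". It also states: "Participants who withdraw from the study will be able to keep their CPAP machine". It does not say whether modem uploads stop at that point.

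On uploads, section 6.0 says in one place: "The device will upload objective adherence data to RedCap each morning following use". Section 5.01 and an earlier paragraph of section 6.0 say that data are uploaded every morning, with no condition of use.

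**The concern.** For a patient with 90 observed days the descriptions agree. For a patient who withdraws they do not. Under section 17.0 read with section 14.0, someone who uses CPAP 5 h/night for 20 nights and then leaves scores 5.0 h. Over a 90-night window the same patient scores 5 × 20/90 = 1.11 h if use then stops. Because leavers keep the machine, their use after leaving is a real quantity that belongs to the 90-day average, and the modem might still record it.

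At stake is the primary between-arm comparison, for which section 17.0 plans a Wald test and a 95% confidence interval. With 10 patients per arm, a few early leavers can move it. The only remedy offered for unequal follow-up is the weighting, and that gives the early leavers less influence.

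**Working it through.** **Inputs.** From the protocol: 20 patients, half per arm (section 2.0), and 90 days of participation (section 9.0). The protocol gives no withdrawal rate, expected adherence or power calculation, so there is no planned figure to reproduce. Every use level and withdrawal count below is assumed. Arm means are unadjusted. The covariates and provider effect of the planned model are left out.

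**Formulas.** Let *h* be a patient's hours up to withdrawal, *d* the nights up to withdrawal, and *r* the hours used afterwards, up to night 90.

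- 90-night mean: (*h* + *r*)/90.
- Unweighted days-observed mean: *h*/*d*. It equals the 90-night mean exactly when *r*/(90 − *d*) = *h*/*d*, that is, when use after leaving equals use before.
- Weighting each *h*/*d* by *d* turns the arm mean into Σ*h*/Σ*d*.

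**One leaver.** If a patient leaves after *d* nights at *u* h/night and then stops, days observed raises that arm's mean over the 90-night value by *u*(1 − *d*/90)/10. For *d* = 20 this is 0.08, 0.23 and 0.39 h at *u* = 1, 3 and 5. For *d* = 60 it is 0.03, 0.10 and 0.17 h.

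**Main example.** Adherers use 5.5 h on 90 nights (495 h each). Four control and two intervention patients use 3 h for 20 nights (60 h each) and withdraw.

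- Total hours: control 6 × 495 + 4 × 60 = 3,210; intervention 8 × 495 + 2 × 60 = 4,080.
- 90 nights, zero use afterwards: 4,080/900 − 3,210/900 = 4.53 − 3.57 = **0.97 h**.
- Days observed, unweighted: (8 × 5.5 + 2 × 3)/10 − (6 × 5.5 + 4 × 3)/10 = 5.00 − 4.50 = **0.50 h**. This is also the true 90-night difference if leavers went on at 3 h.
- Days observed, weighted: 4,080/(720 + 40) − 3,210/(540 + 80) = 5.37 − 5.18 = **0.19 h**.

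The weighted figure lies outside the range from zero use to unchanged use (0.50 to 0.97 h). The reason is visible in the weights: the four control leavers are 40% of their arm but carry 80/620 = 13% of its weight.

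**Other patterns** (leavers stop at night 20; difference in hours, intervention minus control; the unweighted column is also the truth if use continues unchanged):

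| Pattern | 90 nights, zero afterwards | Unweighted | Weighted |
|---|---|---|---|
| 4 control v 2 intervention leavers at 1 h | 1.06 | 0.90 | 0.34 |
| 3 stop per arm at 3 h, only the intervention ones withdraw | 0 | 0.70 | 1.23 |
| 3 per arm at 3 h, all withdraw | 0 | 0 | 0 |
| 4 v 2 leavers at 5.5 h | 0.86 | 0 | 0 |
| 4 v 2 leavers at 6.5 h | 0.81 | −0.20 | −0.08 |

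So the error can run in either direction. The weights distort the difference when leaving is unbalanced and leavers used CPAP less than completers. They are neutral when leaving is balanced or use was equal, and they help slightly when leavers used it more.

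**Unused nights (secondary).** If only mornings after use produced an observed day, unused nights of enrolled patients would also drop out. With 5.5 h per used night, and 75 used nights in the intervention arm against 60 in control, the 90-night difference is 5.5 × 75/90 − 5.5 × 60/90 = 4.58 − 3.67 = 0.92 h. Counting used nights only, it is 0.

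**The case against.** Four objections deserve an answer.

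**Days observed may be the right answer.** A reader might infer that the days-observed figure is biased whenever withdrawal differs by arm, or that zero use after leaving is the truth. The protocol supports neither. Leavers keep the machine and their usual care, so continued use is plausible, and with unchanged use the unweighted figure is exact. In the main example, zeros would then overstate the difference at 0.97 h against 0.50 h. This stands, and the bias claim is conditional for that reason.

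**The unused-nights reading is weak.** A reader might infer that zero nights certainly leave the denominator. Section 17.0 links observation to follow-up time, dropout and missed visits. Two passages say that uploads occur every morning, and the wording about mornings following use can simply mean the next morning. Section 5.02b also acts on lack of use, so non-use has to be recognised there. This stands too: the point is a wording conflict to settle, not a demonstrated loss of data.

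**The weights are optional and do not always harm.** Correct. They are conditional on substantial variability in follow-up, and balanced leaving leaves the difference at 0 in the table. But they are the plan's only stated response to dropout, and they address precision, not the missing nights.

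**This is detail for a statistical analysis plan.** That would hold for coding conventions. Here, however, the protocol itself states the formula and the weighting, and both sit beside a 90-day definition that they do not match. Patients who merely stop using CPAP without withdrawing keep their zero nights on the natural reading, so the gap concerns actual withdrawals, whose number is unknown.

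**Conclusion.** The point holds in conditional form. The stated formula departs from the stated 90-day endpoint for any patient who withdraws early. The arm difference is biased if use falls after withdrawal and withdrawal is unbalanced between arms. The weighting does not repair informative dropout, because it down-weights leavers by a variable measured after randomisation.

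The size cannot be fixed from the protocol. In the main example the same data give 0.97, 0.50 or 0.19 h, against the 1.31 h/night that section 3.05 quotes for behavioral interventions. Those figures rest on 2 to 4 of 10 patients per arm withdrawing at night 20, which is assumed. With balanced withdrawal and equal use there is no effect on the difference. The treatment of unused nights is a secondary clarification.

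Separate and minor: section 9.0 allows enrollment to December 31, 2022. Adding 90 days gives March 31, 2023, which is 30 days after the estimated analysis date of March 1, 2023.

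**What to change.** 1. Define the primary outcome as total hours over one fixed window of 90 nights (30 for the 30-day endpoint), with the same named start point in both arms. Bring sections 5.01, 6.0, 14.0 and 17.0 into line. Sections 5.01 and 6.0 differ on whether the machine arrives at enrollment or within a week. Seven nights without a machine would turn 5.50 h into 5.5 × 83/90 = 5.07 h, though in both arms.
2. Reconcile the upload wording and count a night without use as 0 h for an enrolled patient. Leave out only documented transmission failures, checked the same way in both arms, for example by a device download at the 90-day in-person visit.
3. Keep collecting passive modem data to night 90 after withdrawal from study tasks, in both arms, where consent and authorisation allow.
4. Remove days-observed weighting as the remedy for dropout. Where device data after withdrawal are unavailable, name one primary rule before unblinding: zero use afterwards, with the pre-withdrawal mean as sensitivity analysis, or the reverse. The pre-withdrawal mean reproduces the current unweighted formula.
5. Separately, reconcile the dates in section 9.0.

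The cost is rewording, a line in the consent and authorisation process, slightly more data handling and one extra analysis. One downside is that an undetected modem outage would be scored as non-use: 30 nights at 5.5 h in one patient lowers an arm mean by 5.5 × 30/90/10 = 0.18 h. The study tasks table in section 6.0 lists contact after more than 72 hours without data only for the intervention arm, so the download check must cover both arms.

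### The primary model codes BMI and AHI as indicator variables; entering them as continuous terms would recover a modest amount of precision at no cost

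*Protocol*

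**What the plan says.** Protocol section 17.0 sets out the Aim 1 analysis. The outcome is one value per patient, "the total number of hours of CPAP use divided by the number of days observed for the" individual. On the random part it says: "Linear mixed effects models using random effects will be used to adjust for clustering of patients within sleep provider". On the fixed part it says: "Covariates (fixed effects) will include indicator variables for BMI, AHI, gender, and treatment". The effect is tested with a Wald test using a robust standard error, and "a corresponding 95% confidence interval for the intervention effect will be computed".

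No number of categories and no reason for using indicators is given, and nowhere does the protocol say that BMI or AHI enters as a continuous term. In section 6.0, "OSA severity will be assessed using the apnea-hypopnea index", taken as a value from the polysomnogram report.

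The trial is small. Section 12.0 says: "This study will enroll 20 African American patients of MetroHealth with OSA and their bed partners". Section 2.0 gives equal arms ("Half of the patients will receive optimal" usual care). Section 17.0 adds: "Because this is a pilot study, a power calculation is not provided". Section 13.0 stratifies randomisation by study site only.

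**The concern.** An indicator variable separates groups. Used for BMI or AHI, it treats everyone within a group as alike and discards the differences inside it. If those differences predict CPAP use, the discarded part returns to the residual variance and widens the interval for the treatment effect.

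Indicators are sometimes used to mirror stratification factors, but neither BMI nor AHI is one here. With 10 patients per arm and no power calculation, the width of the interval largely determines what the pilot can tell a later trial, so a precision loss that can be avoided for free is worth avoiding.

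**Working it through.** The protocol states no power, standard deviation or R² that could be reproduced. The check therefore compares the two codings directly.

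**Inputs from the protocol.** 20 patients (12.0), half per arm (2.0); fixed effects for treatment, gender, BMI and AHI (17.0); AHI of 15 or more at entry (10.0); AHI mean 27, SD 27 among eligible patients (25.0).

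**Assumptions.** BMI and AHI jointly explain a share R² of the variance in CPAP hours, taken as 0 to 0.30. Covariates are normal with a linear effect. Categories are equal in size. The provider random effect and the robust standard error are ignored, so the degrees of freedom are those of ordinary least squares.

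**1. Information kept.** For a normal covariate, a median split keeps 2/π = 0.637 of its explained variance. Three and four equal categories keep 0.793 and 0.861.

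**2. Standard error with a median split of each.** Ratio to linear terms = √[(1 − R² × 2/π) / (1 − R²)].

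| R² | Calculation | Ratio |
|---|---|---|
| 0 | √(1/1) | 1.000 |
| 0.10 | √(0.9363/0.90) | 1.020 |
| 0.20 | √(0.8727/0.80) | 1.044 |
| 0.30 | √(0.8090/0.70) | 1.075 |

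**3. Degrees of freedom.** Linear terms need an intercept, treatment, gender, BMI and AHI: 5 parameters, 20 − 5 = 15 residual. One binary indicator each needs the same 5, again leaving 15. Three categories each need 7, leaving 13. Four for BMI and three for AHI need 8, leaving 12.

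**4. Interval width with finer coding.** The half-width is proportional to t(0.975, df) × √[(1 − R²) × (4/N) × (N − 3)/(N − 3 − q)], where N = 20 and q counts the covariate terms other than treatment. Four categories for BMI and three for AHI, relative to linear terms, give 1.153, 1.164, 1.178 and 1.195 at R² = 0, 0.10, 0.20 and 0.30. Finer coding keeps more information but pays in degrees of freedom, so the two losses trade off.

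**5. Simulation check.** 5,000 trials per setting, least squares, true effect 1 SD. Mean half-widths for linear and binary coding were 1.031 and 1.032 at R² = 0, 0.977 and 0.996 at 0.10 (ratio 1.019), and 0.918 and 0.959 at 0.20 (ratio 1.045). Power was 0.478 and 0.476, 0.513 and 0.504, and 0.571 and 0.529 respectively. The half-width ratios agree with step 2.

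**6. Scale for AHI.** If the entry floor applies to the clinic table, the mean lies 27 − 15 = 12 above the floor while the SD is 27. Even with a floor of zero, the mean is only one SD above it. Both point to right skew.

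**The case against.** The best defence is that the loss is small and its size rests on assumption. The protocol links neither BMI nor AHI to CPAP hours; the predictors of adherence it names in section 3.04 are race, socioeconomic position, early adherence and patients' perceptions. With R² near zero, a binary split costs nothing. The 2/π factor also assumes a normal covariate, which a skewed AHI is not. A median split is the same on the raw and the log scale, so the factor would carry over if log AHI were roughly normal, but the protocol cannot show that. The wording may simply be loose, grouping all covariates under one term. All this stands and keeps the point minor. It does not defend the coding: the sentence as written fixes indicators and gives no reason for them.

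Four stronger readings are tempting, and the document does not support them.

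- *Indicator coding necessarily spends scarce degrees of freedom.* It does so only with three or more categories, and the protocol states no number.
- *Cut-points will be chosen after the data are seen.* They may be in a SAP that is not shown, and section 13.0 limits who knows the arm assignments.
- *The treatment comparison is biased.* Randomisation keeps it unbiased under any coding fixed without reference to the results.
- *The same flaw runs through all of Aim 2.* Section 17.0 says only that those analyses resemble Aim 1's, and no AHI is collected for bed partners.

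**Conclusion.** The point holds as a minor matter of precision. The protocol specifies a less efficient coding for two continuous covariates without a design reason. With a binary split, the standard error is about 2% to 8% larger for an assumed joint R² of 0.10 to 0.30, and no larger at R² = 0. A penalty of 15% to 20% in interval width arises only under a finer coding, such as four and three categories, which the protocol does not mention. These figures assume normal covariates, linear effects and equal-sized categories, and ignore the provider effect; for AHI they are indicative only.

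**What to change.** Replace the covariate sentence in section 17.0 with: *Fixed effects will be indicator variables for treatment and gender, and BMI and AHI as continuous covariates with one linear term each (AHI log-transformed).* The log scale is a judgement based on the skew shown above; it also limits the leverage of very high AHI values among 20 patients. State that the same coding applies to patient outcomes in Aim 2.

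The change costs one sentence. It needs no new data and uses no more degrees of freedom than the coarsest indicator coding.

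### The primary Wald test with a robust standard error does not hold 5% in 20 patients: read plainly, its false-positive rate is about 12% (patient-level) or 22% (provider-clustered)

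*Protocol*

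**What the plan says.** The analysis plan is in section 17.0 of the protocol. The primary outcome is one number per patient, mean daily hours of CPAP use, compared as randomized between two arms of 10.

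- Model: "Linear mixed effects models using random effects will be used to adjust for clustering of patients within sleep provider".
- Fixed effects: "Covariates (fixed effects) will include indicator variables for BMI, AHI, gender, and treatment".
- Test and interval: "A Wald test (with robust estimate of standard error) will be used to test for an intervention effect and a corresponding 95% confidence interval".
- Normality check: "The model assumption that the overall CPAP usage outcome is normally distributed will be tested using the Shapiro-Wilk test".
- Fallback if that check fails and no transformation helps: "an alternative approach will be to use a generalized linear (e.g., Poisson regression) model for the overall adherence (CPAP usage rate").
- Uneven follow-up: a weighted analysis is allowed, "using weights proportional to the number of days observed for each individual in conjunction with the selected model".
- Sample size: "Because this is a pilot study, a power calculation is not provided".

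The Aim 1 hypothesis in section 2.0 is stated in hours: "patients who receive the couple-oriented intervention will use CPAP for more hours per night over 90 days (primary outcome"). Section 17.0 extends the same approach to the Aim 2 scales and moves those that are not normally distributed to a proportional odds model. The table in section 25.0 lists 7 sleep providers in the recruitment pool. The protocol does not say how many of them will contribute patients.

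**The concern.** The sandwich estimator builds the standard error from squared residuals. Fitted residuals are smaller than the true errors, more so where leverage is high, so in a small sample with several covariates the standard error is biased downward. It is also noisy, and a normal reference ignores that noise. Clustering on providers makes both problems worse, because there are then at most about 7 independent contributions to the variance estimate.

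The protocol names this method for 20 patients and says nothing about a correction, degrees of freedom, or whether the robust error is taken over patients or providers. If it is carried out as the words most plainly suggest, a true null effect would be declared significant far more often than 1 time in 20. A pilot's main quantitative product is its interval for the effect, and that interval would be too narrow. The Aim 2 scales analysed in the same way inherit the problem.

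Two smaller points belong to the same paragraph of the plan. The Shapiro-Wilk check is worded as a test of the outcome, whereas the model's assumption concerns residuals. A switch to a log or Poisson model would turn the effect into a ratio, away from the hours-per-night scale of the hypothesis.

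**Working it through.** The protocol gives no type I error or power figure to reproduce. The only nominal level is the 5% two-sided level implied by the 95% interval.

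**Inputs from the protocol.** 20 patients, half per arm (sections 2.0, 6.0, 12.0). Permuted blocks (13.0). Intercept, treatment, BMI, AHI and gender, so p = 5 if BMI and AHI each have one indicator, and a provider random effect (17.0). 7 providers (25.0).

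**Assumed, because the protocol does not give them.** Blocks of 4, all 7 providers contributing, provider intraclass correlation (ICC) 0, 0.05 or 0.10, one binary indicator each for BMI, AHI and gender, and all standard deviations.

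**Hand check, patient level.** In least squares the expected squared residual is σ²(1 − h), with mean leverage h = p/n = 5/20 = 0.25. The uncorrected variance is therefore about 75% of the truth and the standard error about √0.75 = 0.87 of it. The nominal cut-off of 1.96 acts like 1.96 × 0.87 ≈ 1.70. Against a t distribution on 20 − 5 = 15 df, P(|t| > 1.70) is about 11%. Unequal leverage and a noisier variance estimate push this a little higher.

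**Simulation under the null.** About 22,000 trials per scenario, Monte Carlo error about 0.1-0.3 points. Rejection rates at nominal 5% (range over the three ICCs), uncorrected sandwich with the normal reference:

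| Model | Patient-level | Provider-clustered |
|---|---|---|
| Planned mixed model (REML) | 12.2-12.5% | 21.4-21.9% |
| Least squares | 12.3-12.9% | 19.2-19.5% |
| Poisson fallback | 11.0-11.4% | 17.7-17.9% |

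The Poisson runs used a log link, no provider random effect and an outcome clipped at zero. Coverage of the 95% interval is 100% minus these rates: about 78-88% in the mixed model and 82-89% in the Poisson model.

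**Effect of corrections** (K = number of providers; K − 1 = 6 when all 7 contribute):

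| Method | Rejection rate |
|---|---|
| HC1, normal reference | 8.1-8.4% |
| HC1, t(15) | 6.0-6.2% |
| HC2, t(15) | 5.7-5.9% |
| HC3, t(15), least squares | 3.1-3.2% |
| HC3, t(15), mixed model | 4.1-4.5% |
| CR1, normal reference, mixed model | 14.5-15.3% |
| CR1, t(K − 1), mixed model | 8.5-9.2% |
| CR2, t(K − 1), mixed model | 7.8-8.6% |
| Mancl-DeRouen, t(K − 1) | 3.0-3.2% and 3.9-4.2% (two model fits) |
| Kenward-Roger, mixed model | 4.2-4.6% |
| Kenward-Roger, with a t(15) linear model when provider variance is estimated as zero | 5.4-5.6% |

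The zero-variance case occurs in 44-56% of fits.

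**Sensitivity** (mixed model, ICC 0.05; uncorrected patient-level, uncorrected provider-clustered, Kenward-Roger):

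- Outcome clipped at zero: 12.1%, 21.3%, 4.3%.
- Intervention-arm residual SD 1.5 times control: 12.7%, 21.9%, 4.5%.
- 30% of patients observed for only 7-89 days, unweighted: 12.5%, 22.0%, 4.5%.
- The same uneven data weighted by days observed, least squares only: uncorrected patient-level 13.7%, model-based t(15) 6.2%, HC3 with t(15) 3.2%.

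**Cross-check.** Separate mixed-model runs (5,000 per scenario, ICC 0, 0.05 and 0.2) gave 11.1-11.9% patient-level and 21.2-22.8% provider-clustered. With 5 active providers the clustered figure was 24%, and with 3 it was 33%. In separate least-squares runs, dropping all covariates lowered the patient-level figure to 7.8%, and the ordinary model-based t-test held 5.1%. The excess therefore comes from the chosen test and not from the sample size alone.

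**The case against.** The strongest reply is that the sentence does not commit to an uncorrected sandwich or a normal reference. HC2 or HC3 with a t reference is also a Wald test with a robust error, so the wording is compatible with rates from about 3% to 22%. The variant, degrees of freedom and clustering level are details that an SAP could supply. This stands in part: the 12% and 22% describe the plain reading and do not predict what the final analysis must do. But the protocol names a large-sample method for 20 patients, and the usual light corrections do not repair it: HC1 with the normal reference gives about 8%, and provider-level CR1 about 15%, or about 9% with t(K − 1). HC1 and HC2 with t(15) differ little from each other, and both lie only slightly above 5%.

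Second, the sentence follows the Poisson fallback and might govern that model alone. That reading is possible, but the inflation there is similar.

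Third, the provider count, ICC and covariate coding are assumed. This is true. The patient-level figure hardly depends on the number of providers, and fewer active providers make the clustered figure worse.

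Fourth, this is a pilot with no power calculation and no decision tied to the p-value. That limits the harm but does not remove it, because the protocol still plans a hypothesis test and a 95% interval for its primary outcome. The residual check and the change of scale are separate from the inflation and add no weight to it.

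**Conclusion.** The concern holds and should be fixed. Read plainly, the planned test of the Aim 1 hypothesis has a false-positive rate of about 12% with a patient-level robust error (about 1 in 8) or about 22% with a provider-clustered one (about 1 in 5), where 5% is intended. These figures assume no small-sample correction, a normal reference, one indicator per covariate and, for the second, 7 contributing providers. They change little with ICC, unequal arm variances, clipping at zero or uneven follow-up. Adjusting for provider is sound and is not the fault. The consequence is an overstated p-value and a too-narrow interval in the pilot report, not a wrong go/no-go decision.

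**What to change.** In section 17.0:

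1. Keep the provider-adjusted linear mixed model for hours per night, and base the test and 95% interval on the model-based standard error with the Kenward-Roger correction.
2. State a rule for a provider variance estimated as zero. One option is to refit as a linear model with t on 15 df (fewer if BMI or AHI has more than one indicator). Either way of handling that case gives about 4-6%.
3. If a robust error is kept, in particular with the days-observed weights, name the version and reference: HC3 with t on residual df at patient level, or Mancl-DeRouen/jackknife with t on K − 1 df at provider level.
4. Check normality on model residuals.
5. Keep the difference in hours per night as the primary effect, with any log or Poisson model as a sensitivity analysis.

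This takes a few sentences and no new data. The price is a wider interval. In the mixed-model runs the median Kenward-Roger half-width is 35-39% larger than the uncorrected patient-level interval and 65-66% larger than the provider-clustered one (27-29% and 54-56% with the linear-model fallback). If a robust error is kept, HC3 with t is about 50% wider than its uncorrected version, and Mancl-DeRouen with t(K − 1) about twice as wide.
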